# Emergency Medicine Prospective Protocol

restraints at no cost to the participants at the conclusion of the study. To receive a CRS from the study, we will require caregivers to have the restraint installed with the guidance of a certified child passenger safety technician. This will ensure the restraint is installed in accordance with manufacturer specified guidelines.

[name] will be responsible for reporting Adverse Events and Other Reportable Information and Occurrences to the Lurie Children's Hospital IRB and the Project Officer for this grant as required. The timing of reporting of an adverse event by [name] will be dependent on the severity of the event and whether the adverse event was expected (included in the informed consent).

## **7.1.1.1 Data Safety Monitoring Board**

[name] will work with 2 certified child passenger safety technicians to form a data safety monitoring board. If serious misuse is identified, caregivers will receive pre-determined corrective text messages regardless of the treatment condition. If the research assistant has any questions about the potential for a serious misuse, the photograph will be brought to the attention of the data safety monitoring board and reviewed for determination of serious misuse. Communication to caregivers about serious misuse will occur within 2 days of receipt of the photographs by the study team. Illegal behavior depicted in photographs will be protected within the legal rights provided by the Certificate of Confidentiality.

## **8 Study Administration, Data Handling and Record Keeping**

### **8.1 Confidentiality**

Information about study subjects will be kept confidential and managed according to the requirements of the Health Insurance Portability and Accountability Act of 1996 (HIPAA). Those regulations require a signed subject authorization informing the subject of the following:

- What protected health information (PHI) will be collected from subjects in this study
- Who will have access to that information and why
- Who will use or disclose that information
- The rights of a research subject to revoke their authorization for use of their PHI.

All research staff assisting with data collection, entry and analysis will receive training in the appropriate data handling and confidentiality procedures. Staff will be made aware that a breach of confidentiality is reason for dismissal.

### **8.2 Data Collection and Management**

Data will be collected only after written informed consent has been obtained from the participant.

Six primary sources of data exist for this study:

1) Screening process completed by the research coordinator

The screening process will use information that can identify the child of the caregiver participating. The identifiable information that will be collected and stored in the screening/recruitment log and enrollment log is the child's name, medical record number, date of birth, and date of being screened for study. The investigators need to collect this information because it will help us to avoid approaching families who have already participated in the study or decided not to participate. These tracking logs will be stored on an encrypted hospital device and will not be shared with persons not on the study team unless a Lurie HIPAA release form

# Emergency Medicine Prospective Protocol

has been signed.

2) Surveys (screen, baseline, 6- and 12-month follow-ups) completed by the participant  
Caregivers will be approached for screening and baseline survey discretely in the ED waiting room or privately in their child's ED treatment room. We will use a private area, separate from other patients in the ED, for review of the part 1 informational handout and the part 2 informed consent document. Caregivers will be informed of the time commitment and activity on their part necessary for the completion of the research project. Data collection in the ED will be completed privately and confidentially on a study iPad and can be self-administered unless the caregiver prefers to have the research assistant administer the survey verbally. If the survey is administered verbally, the necessary measures will be taken to ensure privacy of response options of the caregiver. Follow-up assessments similarly will be self-administered on study iPads during the 6- or 12-month follow-up visit, unless the participant chooses to complete the follow-up survey prior to the follow-up visit. Then the participant will complete the survey at their convenience and on their own device (e.g., phone, laptop, iPad, etc.).

Children of caregivers enrolled in the study will have information collected about their weight and height at ED recruitment and in-person follow-up assessments. The children will be receiving emergency medical care in the LCH ED. All research staff who will have interactions with children will receive training from [name], a board-certified pediatrician and pediatric emergency physician, related to their interactions with children for the measurement of weight and height as well as the direct observation of the child in the vehicle which they travelled to the ED and at follow-up assessments.

Subject identifiers (i.e., subject ID numbers) will be present on all surveys to link their data to their identifying information. The Qualtrics Research Suite (<http://www.qualtrics.com/>) will be used to collect and store data from the screening survey and part of the 6 month follow-up survey (The Newest Vital Sign survey). The project-specific Qualtrics site is protected with a researcher-designated log-in name and password. The site houses the surveys and compiles data that staff will then transfer to a secured database on the LCH secure network. There are systems in place that prevent the survey from being taken by the same user more than once. No identifying information is collected from participants; so information remains anonymous and in aggregate form. Additionally, Qualtrics has SAS 70 Certification and meets the rigorous privacy standards imposed on health care records by the Health Insurance Portability and Accountability Act (HIPAA). All Qualtrics accounts are hidden behind passwords and all data is protected with real-time data replication. Qualtrics complies with the U.S. and E.U. Safe Harbor Framework and the U.S. and Swiss Safe Harbor Framework as set forth by the U.S. Department of Commerce regarding the collection, use and retention of personal information from European Union member countries and Switzerland. Qualtrics has certified that it adheres to the Safe Harbor Privacy Principles of notice, choice, onward transfer, security, data integrity, access, and enforcement.

Data obtained in the baseline and follow-up surveys will be stored on a password protected, secure server at the University of Michigan. The University of Michigan Center for Health Communications Research (CHCR) has been subcontracted for this R01 to program the surveys, the study website, and the tailoring of web content using the Michigan Tailoring System (MTS) open-source software. MTS does not have any sort of central server that communicates back and forth with a intervention web "site" – so there is minimal security risk in adding it to any project. MTS functions where it takes code generated by CHCR and then uses a library to interpret how to correctly display that code on the intervention site. Baseline, follow-up and intervention data will be coded according to participant ID number. Additionally, a formal review of the survey system and study web "site" is being completed by the University of Michigan Information

# Emergency Medicine Prospective Protocol

Assurance Office (<https://safecomputing.umich.edu/about>). Once completed, the information assurance assessment will be shared with the Information Management and Institutional Review Board teams at Lurie Children's.

All data collected through the University of Michigan and stored on University of Michigan password protected secure servers will be accessible to the study team via a dashboard. Data will be downloaded to password protected secure servers at Lurie Children's for analysis. We will develop databases for the storage of de-identified data. Files will be stored and backed-up using password protected secure file servers at LCH. Multiple imputation may be employed to address missing data due to dropout or inability to complete follow-up (anticipated <20%).

We will minimize the burden of the research assessments through the use of skip patterns. In order to minimize pressure to provide the perceived "correct" answer, caregivers will be reminded there are no "right" or "wrong" answers to any of the assessment questions. Caregivers will also be informed that they have the right to skip any question that makes them uncomfortable or that they do not wish to answer. They will be informed of their right to withdraw from the study at any time without penalty. Study staff will be trained to respond to emotional distress and to discuss concerns and issues with the project manager, [name], and in her absence, [name] or [name].

We will also have a Certificate of Confidentiality (CoC) from The Eunice Kennedy Shriver National Institute of Child Health and Human Development to protect study participants' data regarding illegal behaviors captured within any of the survey from subpoena and to conserve their own right to request release of their data for their own purposes.

Data collection from all surveys will occur electronically according to the information presented above, unless there are technical problems during the study. To account for technical issues, paper copies of surveys will be used to complete any data collection needed with participants. Data collected via paper will be transferred to the secure online systems as soon as possible by a trained research team member and the paper documents will be shredded afterwards.

Subject identifiers (i.e., subject ID numbers) will be present on all surveys. The subject identifiers will be used to link information to each participant as opposed to using unique identifying information. When patients enroll in the part 2, baseline phase of the study, names will be linked to individual ID numbers in this secure online database created by CHCR, which will be kept in a restricted access folder on a secure server at the University of Michigan. Data exported from the University of Michigan servers for future data analysis will be de-identified before saving to a password-protected folder on secure network at LCH.

3) Monthly photo submissions and text messages from caregivers of their child as they normally ride in their vehicle

Caregivers will submit photos of their child as they normally ride in their vehicle once a month to the study team. Text messages will be sent and photographs submitted to the study team through a third party platform called Twilio (Twilio Inc., San Francisco, CA) (see [www.twilio.com](http://www.twilio.com) for information about Twilio and its privacy/security policies). Twilio will transmit messages and store links to the MMS (photograph submission) and SMS (text message) content on Twilio servers. Twilio will save the image files to an AWS Server. The Twilio link to the MMS message files will be deleted with an API command sent each day at midnight Eastern Time. MMS files are deleted from the AWS Server after 30 days but will not be searchable after the MMS file link is deleted at midnight. SMS file records will be deleted with an API command sent at the conclusion of the

# Emergency Medicine Prospective Protocol

caregiver's participation in the study (i.e., 1 month after completion of the 12-month follow-up). This will ensure we have a complete record of communication sent to them by the study team.

The study team will make every effort to keep data safe and secure. The University of Michigan Center for Health Communications Research has been subcontracted for work on this project. A formal review of the study website is being completed by the University of Michigan Information Assurance Office (<https://safecomputing.umich.edu/about>). Data submitted to Twilio will be transmitted by Twilio to the University of Michigan and saved at the University of Michigan in password-protected folders on a secure network. Only study team members will have access to data.

Data collected for the study through the University of Michigan systems will be downloaded to Lurie Children's and stored in a password protected folder on a password-protected, secure network. All photos will be de-identified – meaning faces will be blurred – when saved to Lurie Children's network. Photos will be deleted from the University of Michigan secure server once they are successfully saved to Lurie Children's network.

*Tango Card- The gift card distribution will be handled using Tango Card™, an electronic gift card distribution software. Tango Card™ will send an email to participants each time a gift card is earned for this study. They will be able to redeem the gift card at a major retailer of their choice. Tango Card™ does not sell or distribute customer email addresses to any third party and Tango Card™ treats all personal data as completely confidential.*

We will also have a Certificate of Confidentiality (CoC) from The Eunice Kennedy Shriver National Institute of Child Health and Human Development to protect study participants' data regarding illegal behaviors captured within the digital photographs from subpoena and to conserve their own right to request release of their data for their own purposes. The CoC will protect all digital photographs collected during the study.

4) Child Passenger Safety Score (CPaSS-D) and (CPaSS-R) used by the research assistant for direct and remote observation of the Tiny Cargo check-ins (car seat inspection)

The CPaSS electronic survey tool will be used by research assistants to observe and record assessment scores for the Tiny Cargo check-ins each month that a participant is enrolled in the study. The CPaSS tool will be used either in direct observation with a family or via photos submitted electronically via text message to the study team.

CPaSS observations recorded from review of the digital photographs will be collected in surveys on the Northwestern University portal to the Qualtrics survey platform that contain study-specific codes only. Qualtrics will house the data for the CPaSS assessments and will only use a subject identifier (ID number) to connect the participant's data with their information. No unique identifying information will be collected within this assessment tool. When it is exported from Qualtrics, the data will be saved to a secure folder on the LCH secure network.

5) Audio recordings of the MI counseling sessions (conducted at the baseline visit, and/or Month 7/8 via phone)

Although the focus of this study is not on child abuse, because of the nature of the study, caregivers may disclose information that raises concerns for potential child abuse or neglect during the MI counseling sessions (baseline visit and/or phone session). The consent form will contain a statement regarding the mandatory reporting requirements. Staff training will include review of the study protocol regarding the limits of confidentiality, liaison with ED staff (i.e., clinical

# Emergency Medicine Prospective Protocol

care providers) regarding concerns for potential child abuse or neglect, and circumstances in which it may be necessary to report suspected child abuse or neglect to Illinois Department of Children and Family Services (DCFS). Study procedures will also require staff to immediately contact [name] in cases where these concerns arise.

MI counseling sessions for this study will be conducted/facilitated by the RA with participants and will be audio recorded (with signed permission from participants) in order to ensure the fidelity of the intervention. Staff will be trained to administer the TCBD MI counseling intervention in a specific way and in order to ensure all staff are conducting and coding the data correctly, it is necessary to audio record this portion of the study. Audio recordings of MI counseling sessions will not include the caregiver's name or any information that could be used to identify them. Audio records will be coded only with the research assistant ID, subject ID and study name, and date of the session. Taping will be done using a LCH secure device (study iPad and/or study iPhone), and counseling sessions will be immediately uploaded to a password protected LCH server folder and deleted from the device. All audio recordings will be destroyed from the LCH server as soon as fidelity monitoring is completed.

6) Paper study documents --consent forms, proof of payment and study follow-up information  
All paper study documents (e.g., consent forms, payment forms, follow-up related contact forms, etc.) with patient identifying information will be kept stored in locked file cabinets separate from any data collection forms. Each file cabinet will have a unique key and will be kept within a locked office, within a locked suite and within a locked building accessible by LCH badge only.

Subject identifiers (i.e., subject ID numbers) will be present on study-related forms. The subject identifiers will be used to link information to each participant. When patients enroll in the part 2, baseline phase of the study, names will be linked to individual ID numbers in this database, which will be kept in a restricted access folder on a secure server.

Signed consent forms will be kept in a locked file cabinet in a locked research office at the study site. All information collected as part of both research projects will be accessible only to research staff who have completed mandatory training in the protection of human subjects.

Follow-up contact information that the caregiver provides to the study team will be stored separately with a unique study identifier to link information. The dataset with identifiers will be destroyed as soon as possible after the completion of 12-month follow-up. Caregiver identifiers (contact information) will be retained for the purposes of follow-up.

The study team will follow the federal guidelines as the necessary time that all study materials will be kept following the conclusion of the study recruitment and analysis period.

## Blinding for purposes of data collection:

This is a unique single-blinded study where a portion of the study will include blinding of study team members. The blinding will not include the Principal Investigator or the Study Coordinator. Also, participants will know which group they are enrolled in as the consent form states the study groups as well as the extent of study involvement based on which group you are enrolled in.

The portion of the study that includes blinding are the monthly photo submissions that participants will send us via text message over the course of 12 months.

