## 2 Study Objectives

The proposed randomized, adaptive trial will test the efficacy of a selective intervention, *Tiny Cargo, Big Deal* (TCBD), to improve child passenger safety among caregivers who are not adherent to current national recommendations. The TCBD intervention, grounded in Self-Determination Theory (SDT) and developed as a part of [name] K23 award, consisted of a brief motivational interviewing (MI) session in the ED and a mailed brochure tailored on child age, size, and restraint use. TCBD proved feasible and acceptable with *significant promise for improving child passenger safety behaviors* at 6-month follow-up. We have enriched TCBD based on pilot participant feedback to include a streamlined ED counseling session, new eHealth components, and one booster MI session delivered by phone. To replace the paper brochures, we have designed a prototype mobile friendly web "site" that has shown positive results in usability testing. The study site will be optimized for mobile devices and provide to the intervention group with continuous access to *personalized, precise* child passenger safety information. We will augment the intervention with tailored short message service (SMS) communications (i.e., text messages) that facilitate bi-directional flow of information after the ED visit.

We hypothesize that a precision prevention intervention (TCBD) that provides tailored child passenger safety education and personalized skills for restraint use in a manner that supports autonomous motivation will be more efficacious than universal approaches (laws/national guidelines) for realizing correct use of a size-appropriate child passenger restraint. The primary outcomes, size-appropriate restraint use and the Child Passenger Safety Score (CPaSS), will be assessed with direct observation at scheduled, in-person appointments and remote observation of digital photographs submitted by caregivers in response to unscheduled text messages.

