## Monthly Photo Requests:

Both groups will be asked to send the study team photos of how their child normally rides in their vehicle and will be paid the same incentive amounts. However, if major misuse or errors are visible within the photos that participants submit, then the text messages sent to participants will vary slightly depending on which group you are enrolled in.

- 1) control group --they will receive a concise text message for any major misuse/errors that are visible and how to adjust for it. Non-critical errors will not elicit a direct text message response from the study team.
- 2) TCBD intervention group --they will receive a slightly longer text message that is framed within the spirit of motivational interviewing that addresses the major misuse/error and possible solutions to adjust for it. They will also receive tailored messages for any non-critical misuse/errors.

\*\* See section 9 (Supporting documents) of the IRB application for an excel file that serves as a library of text messages that will be provided to participants when major misuse/errors are visible (in-person or via photos) based on the study group they are enrolled in. This is a sample of the messages that will be used and sent out, but not meant to be a comprehensive library of messages. The RC will use their discretion when reviewing misuse/errors and adjusting messages as needed.

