## 3.4 Study Endpoints

### 3.4.1 Primary Study Endpoint

The primary outcomes (size-appropriate CRS use and CPaSS) will be assessed in-person at Month 12. The secondary outcome, the CPaSS trajectory, is a measure of correct and consistent restraint use in response to the intervention and will be assessed by scoring photographs submitted by caregivers (Months 1-5; 7-11) and collected by the study team (Months 6 and 12). Photographs will be scored using the CPaSS tool by research team members blinded to the treatment group.

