[name] will be responsible for providing training to all research staff conducting assessments regarding procedures for managing anticipated issues. Specifically, this training will include information regarding warning signs of distress that occur as a result of the surveys and the means for addressing such issues and minimizing distress. Staff will receive training from [name] in management procedures if a caregiver reveals child abuse/neglect or concerns about safety. Staff training will include review of the study protocol regarding the limits of confidentiality, liaison with ED staff (i.e., clinical care providers) regarding concerns, and circumstances in which it may be necessary to report suspected child abuse or neglect to the Illinois Department of Children and Family Services (DCFS). Study procedures will also require staff to immediately contact [name] in cases where these concerns arise. [name] will be responsible for training in Motivational Interviewing (MI) techniques. The project manager will facilitate monitoring for fidelity to the intervention throughout the course of the study by reviewing and scoring audio recordings from MI sessions. A consultant with mastery of MI techniques and teaching of MI will provide feedback and additional training as needed.

The digital photographs submitted by caregivers will be reviewed by a trained research assistant within 24-48 hours of the submission. The research assistant will score the photographs with the Child Passenger Safety Score and determine which feedback messages will be returned to the caregivers in the intervention group. For the development of the CPaSS Tool, in collaboration with [name] and child passenger safety technicians, [name] has developed a list of child passenger safety behaviors that constitute serious misuse (for example, having a car seat sitting on the vehicle seat but not attached in any way). To offer greater protection in a crash to all children involved in the study whose caregivers have not obtained a size-appropriate child restraint system at the 6- or 12-month follow-up assessment, we have budgeted to provide size-appropriate

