# Emergency Medicine Prospective Protocol

Study team members that directly enroll participants in the ED will not be able to review any monthly photo submissions from those families. They will only be able to review and score (using the CPaSS tool) photo submissions of families that they did not directly enroll, so they are blinded to which study arm the family is enrolled in.

Study team members that are only assisting with the review and scoring (using the CPaSS tool) of photo submissions each month will be blinded to the study arm the participant is enrolled within. Because they will not be enrolling participants within the ED and they will not have access to the study dashboard where the photos are submitted, these study team members will remain blinded throughout the course of the study and will only provide scoring based on what they observe within the photos. These study team members will relay the scoring of all photo submissions to the rest of the team to record within the database and the additional study team members will send out text message feedback to the families based on any major misuse/errors that are visible within the photo submissions.

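### Live Month 6 and Month 12 check-ins, which supply the observer-rated primary outcomes, have no stated blinded scorer or score lock

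*Combined protocol and SAP*

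**What the plan says.** **Scope of blinding.** Section 8.2 (Blinding for purposes of data collection) states: "The portion of the study that includes blinding are the monthly photo submissions". Its working rules concern photographs only. Of staff who enrol families it says: "They will only be able to review and score (using the CPaSS tool) photo submissions of families that they did not directly enroll". Of scoring-only staff it says: "they will not have access to the study dashboard where the photos are submitted"; other team members then send the feedback. The Principal Investigator and Study Coordinator are outside the blind, and participants know their group.

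**Primary outcomes.** Section 3.4.1: "The primary outcomes (size-appropriate CRS use and CPaSS) will be assessed in-person at Month 12". Aim 1 in section 2, section 3.2 and Table 1 in section 3.3 give Months 6 and 12; sections 2.1, 3.4.1 and 6.2 give Month 12. The check-in is run by the RA at Month 6 (5.1.3) and the RC at Month 12 (5.1.4), with CPaSS as the tool. Both sections allow photographs or video chat instead. Section 3 (6- and 12-month follow-up visits) gives the RA a motivational-interviewing script or a control script, by arm, when major errors are seen at a check-in.

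**Photographs.** Section 3.4.1 places them under the secondary trajectory outcome, includes those "collected by the study team (Months 6 and 12"), and says that blinded team members score them. Section 2 also counts towards the primary outcomes "remote observation of digital photographs submitted by caregivers in response to unscheduled text messages". Section 7.1.1 has a research assistant "score the photographs with the Child Passenger Safety Score and determine which feedback messages will be returned to the caregivers in the intervention group". Section 8.2, data source 4, pairs CPaSS-D with direct and CPaSS-R with remote observation.

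**The concern.** The written safeguard covers the monthly photographs, which mainly serve a secondary outcome. The live ratings that supply the primary outcomes have none. Since caregivers know their group, the assessor is the remaining place where knowledge of the arm can be kept away from the rating.

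The procedure itself brings the arm into the check-in: if major errors are seen, the script depends on the arm, and nothing says that the score must already be fixed. The roles that run check-ins (RA, RC) are also the roles that counsel TCBD families (RC in section 3.2, RA in section 8.2, data source 5).

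If an assessor who knows the arm is more lenient towards counselled families, part of the difference between groups on the primary outcomes would be read as efficacy. CPaSS is a structured tool (5.1.2), which limits lenient scoring without excluding it. Size-appropriate use is probably less open to it than CPaSS.

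**Working it through.** **Step 1. What is stated for each mode at Months 6 and 12**

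| Mode | Scorer | Blind stated? | Score fixed before arm-specific feedback? |
|---|---|---|---|
| In person | RA (Month 6), RC (Month 12) | No | Not stated |
| Video | As above | No | Not stated |
| Photograph | Blinded team members (3.4.1) | Yes in 3.4.1; 8.2 speaks only of monthly photographs | Scoring and sending separated for scoring-only staff (8.2) |

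The gap is in the first two rows.

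**Step 2. The passages on photographs**

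- *Which outcome they feed.* Section 2 (Aims), section 3.2, Table 1 and section 3.4.1 all make photograph scoring secondary. The sentence in section 2 that counts texted photographs towards the primary outcomes stands alone.
- *Who chooses the feedback.* Section 7.1.1 has the scorer determine the intervention group's messages. Those differ by arm; of the TCBD group, the Monthly Photo Requests text says: "They will also receive tailored messages for any non-critical misuse/errors". This implies a scorer who knows the arm, though section 7.1.1 does not say so. Section 8.2 gives sending to others.
- *Whether a photograph can be a primary score.* Sections 5.1.3 and 5.1.4 allow photo check-ins, and section 4.3 describes study tasks as fully remote. Whether a CPaSS-R score may then stand in for CPaSS-D is not stated.

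**Step 3. Illustration of size**

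The plan gives no figure for assessor bias. From the documents: control rate 17%, 204 controls and 516 TCBD analysable (6.1; 204 + 516 = 720 = 0.80 × 900), two-sided 0.05 (6.2). Assumed here: no true effect, so 17% in both arms, and a fraction x of TCBD non-users wrongly credited as users.

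As a check on the method, the pooled two-sample z test reproduces the plan's power. Expected group sizes are enhanced 516 × 0.75 / 2 = 193.5 and basic 516 − 193.5 = 322.5. Against 204 controls at 17%, 27.6% on basic gives 80.9% and 29.4% on enhanced gives 83.7%; the plan says above 80% for both.

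Formulas for the illustration:

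- observed TCBD rate p = 0.17 + 0.83x, false difference d = p − 0.17
- s0 = √[p̄(1 − p̄)(1/204 + 1/516)], with p̄ = (204 × 0.17 + 516p)/720
- s1 = √[0.17 × 0.83/204 + p(1 − p)/516]
- chance of a significant result favouring TCBD = Φ[(d − 1.96 s0)/s1]

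With x = 0 this is 2.5%. If only half the check-ins are live, in both arms alike, and photograph scores carry no bias, x is halved.

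| Non-users credited at live check-ins | Live share | x | p | d | s0 | s1 | Chance |
|---|---|---|---|---|---|---|---|
| 2% | all | 0.02 | 0.1866 | 0.0166 | 0.0319 | 0.0314 | 7.2% |
| 5% | all | 0.05 | 0.2115 | 0.0415 | 0.0331 | 0.0319 | 23.2% |
| 2% | half | 0.01 | 0.1783 | 0.0083 | 0.0315 | 0.0312 | 4.4% |
| 5% | half | 0.025 | 0.1908 | 0.0208 | 0.0321 | 0.0315 | 9.0% |

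For CPaSS, the standard error of the difference is √(1/516 + 1/204) = 0.0827 SD. A lenient shift of 0.10 SD gives 1 − Φ(1.96 − 0.10/0.0827) = 22.6% if all check-ins are live. At half live the mean shift is 0.05 SD, which gives 8.8%.

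**The case against.** The strongest reply is that blinded scoring is already in the plan. Section 3.4.1 has photographs scored blind, including those from Months 6 and 12, and section 8.2 can largely be read together with it, since remote check-in photographs are also sent by text message. If most check-ins are by photograph, few primary scores are exposed. This stands. It limits the point to in-person and video scoring and is why the half-live figures are shown. It does not supply a safeguard for live scoring, and the share of live check-ins is not stated.

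Several stronger readings are tempting, but the documents do not support them:

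- *The trial has no blinded assessment.* Sections 3.4.1 and 8.2 say otherwise for photographs.
- *The same person counsels and scores a family.* The texts show overlapping roles. They do not say who does which task for a given family, or how often an assessor would know the arm.
- *The plan is divided on whether photographs are primary.* Four places make them secondary and one sentence in section 2 differs. Sections 7.1.1 and 8.2 (Blinding) concern who scores and who is blinded, not which endpoint the photographs feed.
- *The photo scorer is unblinded.* Section 7.1.1 only implies this. The message library holds a version for each arm, so a scorer could identify errors while someone else sends the arm's version.
- *The Month 6 rating biases TCBD against control because it decides who is re-randomised.* That use does not by itself bias the comparison.

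**Conclusion.** The concern holds for live check-ins. At Month 12, and at Month 6 where it is a primary time point, the observer-rated primary outcomes can be scored by someone who knows the arm, and nothing fixes the score before the arm-specific script comes into play. The photograph passages need aligning in two places: the sentence in section 2, and section 7.1.1 against section 8.2.

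The size of any bias is unknown. The illustration gives 7.2% or 23.2% with all check-ins live and 4.4% or 9.0% with half live, against 2.5% without bias. It rests on assumed crediting rates, no true effect, a 17% rate in both arms, the planned 516 and 204, and unbiased photograph scores. A reader should not take these figures as an estimate of what will happen in this trial; at the low end the effect is small. The finding on the text needs none of them. It should be corrected because the omission is plain and the remedy is cheap.

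**What to change.** 1. **Live check-ins, Months 6 and 12.** Record and lock the CPaSS and size-appropriate-use scores before the arm or the arm-specific script is opened. Where existing staffing allows, assign a team member who did not enrol, counsel or message that family.
2. **Photographs.** Have the blinded scorers already described in section 8.2 rate all Month 6 and Month 12 photographs, including photo check-ins. Report a sensitivity analysis of the primary outcomes using these blinded scores.
3. **Record.** For each primary score, note the mode (in person, video, photograph) and whether the scorer knew the arm.
4. **Wording.** Align the sentence in section 2 with the Aims, section 3.2, Table 1 and section 3.4.1. Say whether Month 6 is a primary time point, and whether a photo check-in (CPaSS-R) may stand in for CPaSS-D in the primary analysis. Align section 7.1.1 with section 8.2 so that the scorer does not choose arm-specific messages.

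The cost is protocol wording plus some scheduling and scoring time. A separate live scorer depends on staffing that the documents do not give; where none is available, the score lock and the record still apply. Caregivers may disclose their group during a live check-in, so the bias is reduced, not removed.
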